5.5.2.3. Rationale for Control Groups

Placebo Control Group

The use of a randomized placebo control group added to established standard of care provides the best scientific evidence of efficacy and safety. The use of a placebo control provides a concurrent comparator group, accounting for not only a placebo effect but a standard of care effect. Notably, accounting for the standard of care effect is critical when designing an outcome-based study conducted globally when there are regional differences in the treatment of subjects with PBC.

Historical Control Group

The available robust historical PBC observational datasets (UK-PBC and Global PBC Study Group) will also be leveraged to provide further comparative evaluation of the clinical benefit of OCA. Each database includes >6000 patients with long-term follow-up.

Comparison of OCA treatment to the historical controls may provide utility in addressing potential bias or confounds associated with the placebo arm. For example, bias associated with the potential addition of commercial OCA and/or differences in long-term standard of care between the treatment arms including ancillary treatments and diagnostics.

Therefore, further evaluation of the effect of OCA will compare OCA treatment versus historical controls, and will be supportive to placebo comparisons (ie, comparisons to historical and placebo controls will be evaluated separately).

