13.1.2. Determination of Sample Size

The target population is subjects who are at higher risk of liver-related clinical complications. Eligible subjects will have a diagnosis of PBC with bilirubin levels $>ULN$ and $\leq 5x ULN$ and/or $ALP > 3 \times ULN$. The following assumptions were used in sample size calculations:

- Exponential survival curves, placebo survival estimate of 0.6 at 8 years with a hazard ratio of 0.60, and total study duration of 10 years (from first subject enrolled), allowing for 4 years of subject accrual and 6 years of follow up.
- Subjects will be randomized in a 1:1 ratio to placebo or OCA.
- The 2 groups will be compared using a 2-sided log rank test at the 5% level of significance.
- Two interim analyses and one final analysis are planned. The first interim analysis will be performed when 50% of the target events are accrued and the second interim will be performed when 75% of the target events are accrued.
- A dropout rate of 10% is assumed

Based on the randomization ratio, significance level, and assumed hazard ratio, a total of 127 events (both groups combined) will provide 80% power to demonstrate a statistically significant difference between OCA and placebo on time to liver-related outcomes, including all-cause mortality.

In addition, based on the remaining assumptions stated above, it is estimated that approximately 428 subjects will be enrolled to attain 127 events.

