will be presented. The hazard ratio and 95% CI will be determined based on a Cox regression model stratified by randomization strata to estimate the magnitude of the effect.

Sensitivity analyses will be conducted limiting to the separate individual historical control databases, ie, UK-PBC Group and Global PBC Study Group. To evaluate the robustness of the propensity score estimations, additional algorithms and factors may be considered.

Although the study is designed as a placebo-controlled study, the DMC may recommend changes to study conduct based on the pre-specified interim analyses (see [Section 13.1.12](#)), including the potential use of a revised primary efficacy analysis. This analysis would compare all subjects in the OCA population, to all control subjects (randomized placebo and historical controls) on time to liver transplant or death (all-cause), using similar statistical methodology as specified above.

Notably, the planned primary analysis would not be revised without prior agreement with regulatory authorities.

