13.1.9. Handling of Dropouts or Missing Data

Subjects who discontinue investigational product are expected to continue in the study until study termination.

Missing data will be assumed to be missing at random. In order to determine the effect of missing data on the analysis, efficacy endpoints will be analyzed using different methods of imputation as described below. In addition, the same analyses for primary and key secondary endpoints based on ITT and PP populations will be performed to assess robustness of analysis results. During the conduct of the study, the DMC may recommend refining the missing data strategy to better address the observed pattern of missing data, based on blinded monitoring of the data.

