13.1.12. Continuous Monitoring and Interim Analyses

Blinded safety reports including the accrual of events, drop outs, and/or loss of subjects to commercially available OCA will be reviewed by the DMC on a regular basis.

Two planned interim analyses of the liver-related outcomes will be conducted using the Lan-DeMets O'Brien-Fleming boundaries ([Reboussin 2000](#)). Both interim analyses will be pre-specified and will occur after accrual of 50% (64 events) and 75% (96 events) of clinical outcome events, respectively.

The DMC will review the available efficacy data in conjunction with detailed safety data and other relevant information to recommend continuation, modification, or cessation (for efficacy) of the study beyond each interim analysis. Modification of the study would not take place without prior agreement with regulatory authorities.

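### Section 13.1.8 lets the DMC, after comparative interim looks, recommend (with regulators' agreement) a primary analysis with a different endpoint and a pooled historical control, outside the planned error control

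*Protocol*

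**What the plan says.** The planned primary analysis (Sections 6.1 and 13.1.3) compares OCA with randomised placebo in the ITT population on time to the first adjudicated event of the full composite.

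The last two paragraphs of Section 13.1.8 add a contingency: "the DMC may recommend changes to study conduct based on the pre-specified interim analyses", with a changed primary analysis named as one possibility. That analysis would compare all OCA subjects "to all control subjects (randomized placebo and historical controls) on time to liver transplant or death (all-cause"). The section ends by requiring prior agreement of regulatory authorities before the primary analysis is revised.

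Section 13.1.12, to which this text refers, places the looks at 64 and 96 events with Lan-DeMets O'Brien-Fleming boundaries. It says of those looks: "The DMC will review the available efficacy data in conjunction with detailed safety data". The DMC may then recommend continuing, modifying or stopping for efficacy. Section 13.3 gives the DMC tables by treatment column under dummy labels and lets it unblind individual subjects.

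Elsewhere, historical comparisons are supportive. Section 5.5.2.3 says "comparisons to historical and placebo controls will be evaluated separately". In Section 13.1.10, transplant or death against placebo is step 3 of the hierarchy, after the primary endpoint and MELD ≥ 15.

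**The concern.** The trigger for changing the primary question is an analysis that compares efficacy between arms. If the composite looks weak at 64 or 96 events while transplant or death looks better, the text permits a recommendation to move the primary test to the second. Endpoint and comparator would change together, and both changes could be prompted by the data on which the new test is then run.

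Three things are at stake.

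- Section 13.1.10 claims study-wise type I error control for a fixed sequence. That claim does not cover a sequence whose first step can be replaced after a look at results.
- The event target, power and boundaries were derived for the composite against placebo. Section 13.1.8 states no event target, significance level or switching rule for the alternative.
- Non-randomised controls, whose biases Section 13.1.8 itself acknowledges, would enter the primary result.

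**Working it through.** **1. The plan's own figures, and what they cover.** Inputs from Section 13.1.2: "The 2 groups will be compared using a 2-sided log rank test at the 5% level of significance"; "placebo survival estimate of 0.6 at 8 years with a hazard ratio of 0.60"; "allowing for 4 years of subject accrual and 6 years of follow up"; 1:1 allocation; 10% dropout; 80% power.

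- Events, Freedman: (1.960 + 0.842)² × [(1 + 0.6)/(1 − 0.6)]² = 7.849 × 16 = 125.6, so 126. Schoenfeld for a fixed design: 4 × 7.849/(ln 0.6)² = 120.3, so 121. The stated 127 is consistent.
- Bounds from Lan-DeMets O'Brien-Fleming spending at 64/127, 96/127 and 1, with 0.025 per side: Z = 2.949, 2.348, 2.016. Group-sequential power at 127 events is 0.813 (Schoenfeld drift) or 0.797 (Freedman drift).
- Sample size: λ for placebo = −ln(0.6)/8 = 0.0639 per year; λ for OCA = 0.6 × 0.0639 = 0.0383. With uniform accrual over 4 of 10 years, P(event) = 1 − (e^(−6λ) − e^(−10λ))/(4λ), giving 0.398 and 0.263, mean 0.331. Then 127/0.3308 = 384, and 384/0.9 = 427, against 428 stated.

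These figures reproduce. Every one of them is for the composite against randomised placebo.

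**2. Error if the interim can choose the primary.** Let Z₁ be the composite statistic and Z₂ the alternative. Under no effect both follow Brownian paths in information time, with correlation ρ between them. The documents do not give ρ, so 0.2 to 0.9 is an assumption. Further assumptions are unbiased historical controls and equal information fractions for both analyses. One-sided error in favour of OCA, final test at 1.96, 2,000,000 simulated pairs per setting:

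| ρ | larger Z kept at 50% | larger Z kept at 75% | switch only if Z₁ < 1 at 75% |
|---|---|---|---|
| 0.2 | 4.4% | 4.7% | 4.2% |
| 0.6 | 3.9% | 4.2% | 3.4% |
| 0.9 | 3.2% | 3.4% | 2.7% |

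The nominal value is 2.5%.

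**3. With the group-sequential bounds.** Early stopping on the composite is now included and the final bound is about 2.016. Without a switch the error is 2.5%. For ρ from 0.3 to 0.9 it is 4.3% down to 3.3% (larger Z at the second look), 4.3% down to 3.2% (larger Z at the first look), and 3.9% down to 2.7% (switch only if Z₁ < 1 at the second look).

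**4. If the historical controls are biased.** Under the same bounds and rules, an assumed shift of the final Z₂ by 0.5 standard errors in favour of OCA gives about 4% to 8%. A shift of 1.0 gives about 9% to 17%. The documents give no basis for the size of the bias, so these show direction only.

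**The case against.** **The DMC only recommends, and regulators must agree.** This is true, and Sections 13.1.8 and 13.1.12 both say so. A reader might infer an automatic switch, or one in the sponsor's sole power; the text supports neither. The condition settles who approves the change. It does not alter what prompts the proposal, and it does not restore the error rate.

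**Section 5.5.2.3 describes the default and 13.1.8 a contingency.** This also stands. A reader might infer that pooling the controls contradicts the statement that they are evaluated separately. A default plan and an explicit conditional departure can coexist, so this is not a contradiction. It does show that the departure promotes a supportive comparison to primary.

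**Section 13.1.9 is about something else.** There, DMC changes are "based on blinded monitoring of the data", but only for the missing-data strategy. A reader might infer a general rule of blinded change that 13.1.8 breaks. No such rule is stated, so the contrast is one of wording.

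**The simulated rules are not in the protocol.** Correct. No interim comparison with pooled controls is specified, although transplant and death by arm could be among the efficacy data reviewed. Transplant and death are components of the composite and the randomised subjects are shared, so a high correlation is plausible. That favours the lower part of the range.

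**The SAP may set a level.** It may; it is not shown. The point does not rest on missing detail, because the protocol itself fixes the interim trigger, the new endpoint and the new comparator.

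**Conclusion.** The concern holds. The current text allows a change of primary endpoint and comparator prompted by comparative interim efficacy. That change lies outside the error control claimed in Section 13.1.10 and outside the event, power and boundary calculations.

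With unbiased controls, the rise is from 2.5% to about 2.7% to 4.7% one-sided at 1.96. It rests on the assumed correlations and switching rules. The amount is uncertain, but the direction is the same in every setting tried. Bias in the historical controls in favour of OCA would add to it.

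A reader might go further and infer that the trial's type I error is uncontrolled as planned. The documents do not support that: if the option is never used, the planned test keeps its level.

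**What to change.** In Section 13.1.8, delete the option to revise the primary analysis on the basis of the interim analyses. Keep OCA against pooled controls on transplant or death as a supportive analysis.

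If a fallback is wanted for slow accrual or loss to commercial OCA, write it into the protocol before the 64-event look. Base its triggers only on blinded pooled data: the pooled event rate, already reviewed quarterly under Section 13.1.2.1, and the number starting commercial OCA, already in the blinded reports of Section 13.1.12. State its significance level and event target.

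The cost is a reworded paragraph and the loss to the sponsor of a late rescue option informed by results.

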13.1.9. Handling of Dropouts or Missing Data

Subjects who discontinue investigational product are expected to continue in the study until study termination.

Missing data will be assumed to be missing at random. In order to determine the effect of missing data on the analysis, efficacy endpoints will be analyzed using different methods of imputation as described below. In addition, the same analyses for primary and key secondary endpoints based on ITT and PP populations will be performed to assess robustness of analysis results. During the conduct of the study, the DMC may recommend refining the missing data strategy to better address the observed pattern of missing data, based on blinded monitoring of the data.

13.1.9.1. Time to Event Endpoints

For the time to event analyses, subjects who do not experience an event will be censored at the time of their last contact. Subjects with no data after randomization will be considered to have an event on Day 1 (first day of investigational product dosing).

For analyses of the percentage of subjects with an event, subjects with no data after randomization will be considered to have an event.

All time to event endpoints include only adjudicated events. Sensitivity analyses may consider all events regardless of adjudication. Events with discrepant adjudication will be analyzed using both results.

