8.4.2. Reasons for Mandatory Discontinuation of Investigational Product

8.4.2.1. Liver Transplantation

Subjects who undergo a liver transplant during the course of the study must discontinue investigational product and discontinue the study visit schedule. However, these subjects should be encouraged to consent to the semiannual telephone contact and/or continued record review only to allow for secondary outcome events data to be collected.

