Early Termination	Discontinued	Withdrawn	No additional visits except EOT/EOS	Combined Visit, Completed as close as possible to last dose IP	
Treatment Discontinuation^b	Discontinued	Active	Regular Visit Schedule	Complete as close as possible to last dose IP	Complete at Final study visit
	Discontinued	Semiannual contact ^c	Telephone contact every 6 months (± 2 weeks)	Combined Visit, Completed as close as possible to last dose IP	
	Discontinued	Record review only ^c	Record review only	Combined visit Completed as close as possible to last dose IP	
Sponsor Termination	Discontinued	N/A	No additional visits except EOT/EOS	Combined visit Completed as close as possible to last dose IP	
Pregnancy	Interrupted	Retained	Regular Visit Schedule	Complete as close as possible to last dose IP	Complete at Final study visit
	Discontinued	Complete per the above scenarios - Early Termination or Treatment Discontinuation			
Lost to Follow-up	Discontinued	LTF	None	Unable to complete due to LTF status	

EOS = end of study; EOT = end of treatment; IP = investigational product

^a Refer to [Section 7.1.2](#) Schedule of Study Procedures, [Table 2](#) for all procedures and evaluations required at the End of Treatment and End of Study Visits.

^b Includes initiation of commercially available OCA.

^c Outcomes data to be discussed or collected include data related to adjudicated hepatic and cardiovascular event-related data. No additional data (e.g. AE, concomitant medication, etc) data will be collected, except as indicated in [Section 12.1.8](#).

Some assessments noted below may be omitted if they have been completed within the 6 months (or the timeframe otherwise specified) and so long as safety issues do not warrant repeat testing.

Prior to the EOT/EOS Visit:

If possible to do before the visit, when scheduling the EOT/EOS visit, reiterate dosing instructions and advise the subject:

- If applicable, NOT to take investigational product on the morning of the next visit, and
- To bring the investigational product bottle(s); if applicable, s/he will dose at the clinic, and
- To fast overnight (at least 8 hours) prior to the next visit. Fasting is required prior to all study visits, but water is permitted.

During the EOT/EOS Visit:

- Perform a physical examination (including smoking and alcohol consumption habits).
- Perform assessment for calculation of Mayo Risk Score.
- Perform assessments for calculation of Child-Pugh Score.

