13.1.4. Key Secondary Efficacy Analyses

The key secondary efficacy endpoints will compare OCA to placebo on the following:

- Time to first occurrence of MELD score ≥ 15
- Time to liver transplant or death (all-cause)

- Change from Baseline in total bilirubin at end of study
- Change from Baseline in ALP at end of study

The key secondary efficacy analyses will compare OCA to placebo in the ITT population with respect to the key secondary efficacy endpoints. Only adjudicated events will be included in time-to-event analyses. The comparison (hypothesis testing) will be conducted as specified in [Section 13.1.10](#) in a sequential closed testing gate-keeping procedure, provided that the primary efficacy endpoint comparison is statistically significant in favor of the OCA treatment group. If the primary comparison is not statistically significant then comparison of the secondary endpoints will be considered as descriptive and exploratory. This procedure controls the study-wise type I error.

The 2 treatment groups will be compared using the same methodology as specified for the primary efficacy analysis ([Section 13.1.3](#)). The same analyses for key secondary efficacy endpoints will be performed for PP population as a sensitivity analysis.

Analyses of change from Baseline to end of study in ALP and total bilirubin will be compared between treatment groups using analysis of covariance (ANCOVA) with change from Baseline as the dependent variable including treatment group and randomization stratification factor as fixed effects and the Baseline values as a covariate. The same analysis will be carried out using percentage change from Baseline as the dependent variable.

Descriptive statistics of the laboratory values will be summarized by treatment group. The results, change from Baseline, and percentage change from Baseline values as well as estimates of least-square means, standard errors, and 95% CIs will be presented by treatment group. Estimates of the mean difference between treatment groups, the standard error of the difference, and 95% CI of the difference will be presented.

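### Censoring at last contact counts time when MELD is no longer measured as MELD-free time, which understates MELD ≥15 risk and can bias the first key secondary test in either direction

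*Protocol*

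**What the plan says.** Section 13.1.9.1 states that "subjects who do not experience an event will be censored at the time of their last contact". It makes no exception for endpoints that need a test. Section 13.1.4 lists "Time to first occurrence of MELD score ≥ 15" as the first key secondary endpoint, analysed like the primary, and Section 13.1.10 tests it as step 2 at two-sided 0.05.

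Section 12.2.7 derives MELD from serum chemistry and coagulation at screening and quarterly visits. Three routes keep a subject in contact without those visits:

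- **Telephone only** (Section 8.4.3; Table 7 in Section 9.7.18): consent is changed to a call every six months.
- **Record review only** (same places): no visits and no calls, but continued access to medical records.
- **After transplant** (Section 8.4.2.1): subjects "must discontinue investigational product and discontinue the study visit schedule", and are encouraged to accept calls or record review.

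Table 7, footnote c, says that calls and record review collect data on adjudicated hepatic and cardiovascular events. Beyond that, with one cross-referenced exception for serious adverse events, "No additional data (e.g. AE, concomitant medication, etc) data will be collected". No blood sampling is scheduled in these modes.

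**The concern.** A subject counted as at risk for MELD ≥15 should be one in whom it could be detected. Under the stated rule, someone who stops visits in year 2 and is telephoned until year 8 contributes six years of MELD-free time with no scheduled MELD. A transplanted subject without an earlier MELD ≥15 stays at risk while living with a new liver, because transplant is not an event in the MELD-only endpoint.

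This amounts to imputing no event wherever MELD is unmeasured. It fits poorly with Section 13.1.9, which assumes that missing data are missing at random.

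What is at stake is a confirmatory test: step 2 decides whether steps 3 to 5 can be tested. Time to varices, which relies on endoscopy, has the same problem but lies outside the hierarchy.

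**Working it through.** **The plan's own figures.** They reproduce, so the point concerns the censoring rule and not the sample size. Section 13.1.2 gives "The 2 groups will be compared using a 2-sided log rank test at the 5% level of significance", "Exponential survival curves, placebo survival estimate of 0.6 at 8 years with a hazard ratio of 0.60", "a total of 127 events (both groups combined) will provide 80% power" and "allowing for 4 years of subject accrual and 6 years of follow up".

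- Events, Schoenfeld: 4 × (1.960 + 0.842)² / (ln 0.60)² gives 121. Freedman: (1.960 + 0.842)² × (1.6/0.4)² gives 126. With O'Brien-Fleming-type looks at 64, 96 and 127 events, power is 81.3% (Schoenfeld drift) or 79.7% (Freedman drift).
- Placebo hazard: −ln(0.6)/8 = 0.0639 per year; OCA 0.6 × 0.0639 = 0.0383. With uniform 4-year accrual and 6 further years, the event probability 1 − (e^(−6λ) − e^(−10λ))/(4λ) is 0.398 on placebo and 0.263 on OCA, mean 0.331. Then 127/0.331 = 384, and 384/0.9 = 427, against 428 stated.

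**Effect of the censoring rule.** These inputs are assumptions, not in the protocol: 8-year placebo risk of MELD ≥15 of 20% or 30%; follow-up 6 to 10 years; a share q of subjects leaves laboratory visits at a uniform time in years 0 to 4, independently of risk; no MELD is captured afterwards; contact continues to the end.

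*By hand.* A leaver is measured for about 2 of 8 years on average, so an arm keeps a fraction m = 1 − 0.75q of its MELD events. The hazard ratio then reads about (true HR) × m(OCA)/m(placebo). For 10% on placebo and 20% on OCA, m is 0.925 and 0.850, and 0.850/0.925 = 0.92. A true 8-year risk of 30% reads 30% × 0.925 = 27.8% at q = 10% and 30% × 0.85 = 25.5% at q = 20%.

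*By simulation* (400,000 subjects per scenario, quarterly detection; ranges cover both risks):

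| q placebo / OCA | HR read, true 1.00 | HR read, true 0.60 |
|---|---|---|
| 10% / 10% | 0.99–1.00 | 0.60–0.61 |
| 20% / 20% | 1.01–1.02 | 0.60–0.61 |
| 10% / 20% | 0.91–0.93 | 0.55–0.56 |
| 10% / 30% | 0.83 | 0.50 |
| 20% / 10% | 1.08–1.10 | 0.66–0.67 |
| 30% / 10% | 1.20–1.21 | 0.73 |

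The small departures in the equal-loss rows are simulation noise: censoring at the last MELD shows nearly the same values there. Across all rows that rule returns the true hazard ratio within about 0.02. Where the true 8-year placebo risk is 30%, it reads 28% under the stated rule at 10% loss and 25–26% at 20%; censoring at the last MELD returns 30%.

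*Trials of 428 subjects* with no true effect and 30% risk (3,000 replicates): rejection in favour of OCA, nominally 2.5%, is 2.4% at 10%/10%, 7.8% at 10%/20% and 15.7% at 10%/30%. Censoring at the last MELD gives 2.4–2.7%.

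*Primary composite.* Take the Section 13.1.2 placebo hazard in both arms, assume MELD makes up half of the events, and let 20% of OCA and 10% of placebo subjects lose laboratory visits by year 6. The composite HR reads 0.96; at 30% against 15% it reads about 0.95. The effect is smaller because death and transplant are themselves events there.

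**The case against.** **Record review can still find MELD events.** Footnote c keeps collection of adjudicated hepatic event data, MELD ≥15 is one of the adjudicated events (Section 6.1), Section 8.4.3 retains record access to look for liver outcomes, and adjudication may use hospital records (Section 13.4). This stands in part: not all MELD information is lost. But capture from records depends on when local tests happen to be done, and a call yields no laboratory values. The protocol also does not say whether a record check counts as a contact, so the problem is clearest for telephone follow-up.

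**Few subjects may be affected.** Those who stop investigational product, including those who start commercial OCA, are expected to keep regular visits (Sections 8.4 and 9.2.1), and their MELD is still measured. Transplanted subjects are only encouraged to stay in contact. The only loss figure is 10% dropout overall. All of this stands, so the imbalances above are illustrations.

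**Endpoint-specific censoring is ordinary SAP content.** Section 13 leaves detail to an SAP that is not at hand. But the protocol does not leave this open: it fixes one rule for all these endpoints.

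**The alternative is not assumption-free.** If sicker subjects leave visits, censoring at the last MELD is informative too. The simulation recovers the truth because leaving was made independent of risk.

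**Conclusion.** The concern holds for time to MELD ≥15. Last-contact censoring understates the risk of MELD ≥15 whenever contact continues without systematic MELD measurement: by about 2 percentage points at 10% loss and 4 to 5 at 20%, from an assumed true 30%. It biases the hazard ratio and the step-2 test only if that time differs by arm or is related to risk. Differences by arm are plausible, since pruritus on OCA, commercial OCA and transplant could each act unequally, but the protocol gives no rates and the direction is not fixed.

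A reader might infer more than the documents support:

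- **That the test is biased towards OCA.** Equal, non-informative loss leaves the hazard ratio essentially unchanged, and heavier loss on placebo pushes it the other way.
- **That censoring at death is a defect of the test.** A log-rank or Cox analysis that censors deaths already estimates the cause-specific hazard ratio. Only the descriptive Kaplan-Meier curve differs from a cumulative incidence. Nor is every non-MELD component terminal: after a variceal bleed, for example, subjects continue visits.
- **That progression to cirrhosis shares the problem because it needs elastography or endoscopy.** Sections 9.7.3 and 13.1.5 also accept clinical, laboratory, radiological and biopsy evidence.
- **That post-transplant time enters the primary composite.** It cannot, because transplant ends follow-up for that endpoint as an event.

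**What to change.** Amend Section 13.1.9.1 so that:

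- time to MELD ≥15 is censored at the last MELD assessment and no later than transplant;
- time to varices is censored at the last endoscopy;
- death, transplant and hospitalisation endpoints keep last contact.

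Add one sensitivity analysis of the primary composite that censors event-free subjects at their last MELD assessment. A cumulative-incidence curve for MELD ≥15, with death and transplant as competing events, is an optional descriptive addition.

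The cost is a few lines of text, one extra analysis and slightly less follow-up time in the MELD analysis; no new data or subjects are needed. The amended rule still assumes that leaving visits is non-informative, and the text should say so. It should be settled before unblinding.
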